
B. Specific Aims

Physical inactivity has been identified as a primary contributor of childhood obesity and related diseases,¹⁻⁷ with underserved youth (minority and low-income) at greatest risk of inactivity and its health consequences.^{6,7} However, physical activity (PA) interventions have attained limited-to-no sustained behavior change and thus, have rarely affected targeted physiological or anthropometric health outcomes.⁸⁻¹² Extensive research on sport participation shows highly engaged youth report an affiliation orientation towards PA, identifying social reasons and goals (e.g., being with, and making friends) as their primary motivations for participation, and defining PA competence as achieving these social goals.¹³⁻¹⁵ Despite substantial research noting the importance of social goals on PA-based self-determined motivation¹⁶⁻¹⁸ and participation,¹⁹⁻²¹ PA-based interventions have almost exclusively emphasized approaches centered on constructs related to physical ability (e.g., mastery, self-efficacy).²² To date, little research has focused on understanding the contributions that affiliation orientations (social goals) make toward promoting sustained youth PA.^{23,24} We argue that adolescents' desire for social connections is a primary goal of action underpinning their PA behavior and thus, a key mechanism to target for sustained behavior change. The Active by Choice Today (ACT) program, conducted by our investigative team is one of the first afterschool programs (ASPs) to implement a climate-based intervention based on Self-Determination theory which shows significant improvements in PA in underserved youth.²⁵⁻²⁸ However, limited sustained effects found post-intervention, and data from interviews with ACT staff and youth²⁸ which indicated the presence of several interpersonal barriers (e.g., cliques, teasing) to program effectiveness, suggests additional social climate components still need to be addressed. Systematic observations of ASPs using an observational tool that the PI has developed and tested²⁹⁻³¹ and additional interviews conducted with ASP staff and youth further suggests that targeting youth social goals (e.g., building friendships through PA) and social competencies (e.g., friendship-building skills) may be particularly effective for increasing and *sustaining* the PA of underserved youth. Thus, the proposed study aims to test the feasibility of expanding on the social climate approach of ACT to include three key "PA affiliation orientation" elements for increased and sustained youth PA: 1) Friendships (conceptualizing PA success/competence in terms of having close, mutual relationships with other individuals); 2) Group Belonging (defining competence in terms of feeling liked and accepted by peers), and; 3) Staff Acceptance/Connection (viewing success as feeling connected to, supported, and encouraged by staff).¹³⁻¹⁵ These elements have not been explored in prior research and we believe by enhancing ACT to include them in the resultant ACT2-Connect intervention will lead to sustained positive PA affect, cognitions, and behaviors in underserved youth. Comparison of ASPs receiving the 8-week "Connect" intervention (N=3 ASPs) with ASPs randomized to receive the general ASP curriculum (control condition; N=3 ASPs) will yield preliminary data on the effectiveness of social mediators for improving moderate-to-vigorous (MV)PA and preventing obesity among at-risk youth that can inform future intervention design and youth programming policy. Results of this proposed project will provide the basis for conducting a large scale efficacy trial.

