During year 2, a randomized study (3 intervention and 3 control ASPs) will be implemented to test the feasibility of the intervention approach (N=200 youth). A 12-week follow-up, will test the sustained effects of the social climate intervention on ASP PA climate, youth PA affect, cognitions, behaviors, and BMI

Figure 2. Project Timeline

YEAR 1	YEAR 2
April-Sept 2014 - Interviews/Focus Groups - Observations - Intervention development - ASP program recruitment - Hire and Train Staff	Aug-Oct 2015 - Intervention/Measurement Staff Training - Baseline Data Collection (2 ASPs) - Intervention Implement cohort 1
Sept-Dec 2014 - Pilot Baseline Data Collection - Pilot Intervention (1 ASP vs. 1 control)	Oct-Dec 2015 - Baseline Data Collection for cohort 2 (2 more ASPs) - Intervention Implement (cohort 2)
Feb-Apr 2015 - Post-measures in Pilot ASPs - Data cleaning - Hire Project Staff for Y2	Jan-March 2016 - Post-measures for cohorts 1 and 2 - Baseline data collection for cohort 3 (2 ASPs) - Intervention implement (Cohort 3)
April-July 2015 -Data analysis - Revisions to intervention and measurement - ASP Recruitment for Y2	April-May 2016 - Post-measures cohort 3 - Data Management/ Analysis -Manuscript Preparation

Primary Aim 1 (COMPLETED PHASE 1): Interviews/Focus Groups and Youth Survey

Measures. During year 1, we conducted staff interviews (SIs) and youth focus groups (FGs; youth ages 9-14) in ASP sites to assess 1) key physical (e.g., equipment allocation), structural (e.g., PA preferences, activities offered), interpersonal (e.g., peer behaviors), and intrapersonal supports (e.g., social skills) needed to promote and support a social affiliation orientation towards PA (friendship, group belonging, and staff connection goals), 2) program barriers impeding the development and achievement of these social goals, and 3) input on the design and feasibility of initially- developed program components. Through content analysis (NVivo) we identified key themes related to improving social affiliation that were used to inform the development and implementation of the social climate intervention.

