Targeted Population, Recruitment, and Retention. We aim to recruit 8 middle-school ASPs located within a 70 mile radius of Columbia that serve a primarily underserved population of middle school youth (6th-8th grade) youth. All ASP sites will need to include 1 hour of daily PA/freeplay as one component of the curriculum and be similar in size, percentage of youth per site on free or reduced lunch, race, and gender. One ASP will be asked to participate in the pilot during year 1 and will be compared to a school-based control (youth in the control will receive our general health curriculum administered in their health class during the school day). During year 2, six ASPs will be randomized to the treatment or control (general health curriculum) conditions after baseline data collection. ASP staff and all youth enrolled in the program will be asked to participate in the study. To be eligible, youth must 1) be enrolled in the ASP, 2) have parental consent and assent to participate, and 3) be available for baseline and post-intervention measurement. Youth will be excluded from participation only if they have a medical condition that would interfere with the program's prescribed PA.

Overview of Intervention.

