Drawing from theory and previous correlational^{13-21,64-72} and qualitative research,^{60,61} along with our preliminary studies in ASPs²⁵⁻³¹ we have identified key components for establishing a positive PA social climate that will inform the initial development of the intervention (see **Appendix A**). The intervention will target multiple levels of the ASP setting including staff- and peer- behaviors, program structure (e.g., activities), and the physical environment. Initial essential elements were derived from common themes identified across these levels including: 1) moral, emotional, and social goal-oriented support and skill development (e.g., friendship-building skills) 2) collaborative, cooperative play centered on friendship and informal-fun; 3) equal treatment and access, and; 4) inclusive and engaging for both youth and staff. The primary components of the study include: 1) "Get to know you" sessions aimed specifically at providing youth guided social opportunities to foster friendship building skills, and to promote acceptance, cooperation, contribution (to self and others), and friendship affiliation, and; 2) infusing a novel socially-oriented PA curriculum within ASPs' free play sessions (see **Appendix B**). The intervention will take place during ASPs' 1.5 hour "free play" component 2 times per week for 8 weeks. **[name] (Consultant), [name] (co-I)**, and a staff of **Physical Educators** will assist the **PI** in designing all program activities to meet the criteria of the essential elements.

The "Get to Know You" small group sessions (30 minutes) will be designed to specifically increase friendship building skills, and a value and efficacy for contributing to the health and well-being of oneself and others. It will involve interactive student-led discussions and activities that are designed to foster the intra- and interpersonal assets needed to build and support friendships, group cohesion, and staff connections through PA. For example, in small (staff-assigned) groups, staff will challenge youth with fun team building activities and icebreakers, youth will be encouraged to share ideas (e.g., brainstorm sessions on best methods for teaching friends new activities; how to be a good friend, active listener), personal stories, preferences,

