Primary Aim 2. The second primary aim of the study is to assess whether youth in the intervention demonstrate greater change in the 3 PA social affiliation mechanisms from baseline to post-intervention. Gains in these social mechanisms will be assessed with repeated measures ANCOVA models in which time (baseline to end of program and baseline to post-intervention) is a within subject factor and treatment is a between subjects factor for social mechanism variables measured in both conditions. Analyses will control for demographics, baseline BMI, and any other variables for which there are baseline differences between treatment and control groups (e.g., PYD, depression). To examine overall changes in social mechanisms within the intervention alone, similar repeated measures ANCOVAs will be used, with the between subjects treatment factor dropped. The test of interest will be the within subjects factor of time, with affiliation goals expected to improve over time. Process Evaluation, used to assess the quantity (dose) and quality (fidelity) of program implementation, will also serve as feasibility assessments. Our group has extensive experience with “dose-response” analyses.²⁷ Weekly observational assessments of program facilitation, using standardized ratings developed for other studies,¹⁰¹⁻¹⁰³ will be reduced to a total score, indicating overall fidelity to the activity observed.

Secondary Aims. **Secondary Aims 1 and 2** tests the a-priori hypothesis that youth in the intervention (vs. comparison) will have greater improvements in PA affect, cognitions, and MVPA and healthier BMI (z-score) trajectories (e.g., slight reduction; less increase) from baseline to post-intervention. This study will also provide us with information on the effect size that might be expected to power an efficacy trial after completion of the R21 project. Greater improvements will be assessed with several repeated measures ANCOVA models in which time (baseline to post-) is a within subject factor and treatment is a between subjects factor for PA variables measured in both conditions. Analyses will control for demographics (and BMI for PA outcomes) and other variables for which there are baseline differences between treatment and control groups. Multiple imputation protocols^{104,105} will be used to address missing accelerometer data (see our previous work).²⁵

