Secondary Aim 3 explores whether changes in youth PA social orientations mediate the effect of the intervention on changes in adolescent PA outcomes. This hypothesis will be tested with a

multiple mediator model (estimated path model) where the indirect effect of the program on PA through social mechanisms will be examined. Bootstrapped estimates of the mediated effect will be examined in line with recommendations from methodological research.^{106,107} Both the total indirect effect of all variables together and specific mediated effects of each variable will be examined.

F. Human Subjects

Protection of Human Subjects

Risks to the Subjects

Human Subjects involvement and Characteristics. Subjects will be healthy male and female adolescents and adults. To be eligible, adolescents must 1) be currently enrolled in the afterschool program, 2) have parental consent to participate, and 3) agree to study participation and random assignment, and 4) be available for baseline and post-intervention measurement. Adolescents will be excluded from participation if 1) have a medical condition that would interfere with the prescribed physical activity intervention plan, 2) are developmentally delayed such that the intervention materials will not be appropriate or, 3) are in treatment for a psychiatric disorder. To be eligible, adults must 1) be part of the afterschool staff, 2) have no medical condition or disorder that would limit participation, 3) be available and able to participate in the interviews and/or the intervention phase for the study period.

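### Secondary Aim 3 does not say how the six randomized ASPs enter the mediation model or its bootstrap; resampling youths would make the indirect-effect intervals too narrow if mediators cluster by ASP

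*Combined protocol and SAP*

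**What the plan says.** Under Targeted Population, Recruitment, and Retention, "six ASPs will be randomized to the treatment or control (general health curriculum) conditions after baseline data collection". The study design section gives three ASPs per arm and 200 youths.

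For Secondary Aim 3 the analysis plan names a "multiple mediator model (estimated path model) where the indirect effect of the program on PA through social mechanisms will be examined". On inference it adds that "Bootstrapped estimates of the mediated effect will be examined in line with recommendations from methodological research", with two methods references, and that "Both the total indirect effect of all variables together and specific mediated effects of each variable will be examined".

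The mediators are those of Primary Aim 2, which asks whether "youth in the intervention demonstrate greater change in the 3 PA social affiliation mechanisms from baseline to post-intervention". The repeated-measures ANCOVA for that aim contains time, treatment and covariates, but no ASP term.

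No ICC, design effect, confidence level or resampling unit appears in the documents. The separateness of the sites is discussed only as protection against contamination (Potential Challenges and Alternative Strategies).

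**The concern.** Treatment does not vary within an ASP. Every treatment-to-mediator path is therefore a comparison of three ASPs with three others, and its error includes ASP-to-ASP variation with 6 − 2 = 4 degrees of freedom. A bootstrap that resamples youths as independent leaves that variation out. The same treatment contrast appears in the Primary Aim 2 ANCOVA, so the two sections share the omission. The choice of bootstrap unit belongs to Aim 3 alone.

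Clustering is plausible on the plan's own account: "The intervention will target multiple levels of the ASP setting including staff- and peer- behaviors, program structure (e.g., activities), and the physical environment". Each site also has its own staff and draws on separate schools.

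The Specific Aims section says the comparison "will yield preliminary data on the effectiveness of social mediators for improving moderate-to-vigorous (MV)PA and preventing obesity among at-risk youth", to inform future intervention design. A chance difference between two sets of three ASPs could be carried forward as support for a mechanism.

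**Working it through.** The plan gives no power, ICC or interval width for this aim, so there is no figure to reproduce.

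**Inputs from the documents.** Six ASPs, 3 versus 3; 200 youths, so m = 200/6 = 33.3 per ASP; three mediators. **Assumed:** ICC 0 to 0.10 (the ICC left after covariate adjustment, equal for mediators and outcome residual), partial mediator-outcome slopes 0.1 to 0.3, mediator correlation 0.5, a 95% percentile interval.

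**Step 1: treatment-to-mediator path.** Design effect DE = 1 + (m − 1) × ICC. The standard error is understated by √DE, and the two-sided error of a test that ignores ASP is 2 × [1 − Φ(1.96/√DE)].

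| ICC | DE | √DE | Error |
|---|---|---|---|
| 0.01 | 1.32 | 1.15 | 8.8% |
| 0.02 | 1.65 | 1.28 | 12.7% |
| 0.05 | 2.62 | 1.62 | 22.6% |
| 0.10 | 4.23 | 2.06 | 34.1% |

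This excludes the small-sample penalty: t with 4 df is 2.78 against 1.96, a further factor of 1.42 in width.

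**Step 2: indirect effects under a youth-level bootstrap.** Simulation of 2,000 trials per cell with 500 resamples and no program effect on the mediators. Entries are the percentage of trials whose 95% interval excludes zero, at ICC 0 / 0.02 / 0.05 / 0.10.

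| Slope | Total effect | Each specific effect |
|---|---|---|
| 0.1 | 2.9 / 8.2 / 13.0 / 19.2 | 0.9 / 2.5 / 5.0 / 8.6 |
| 0.2 | 4.5 / 11.8 / 21.6 / 32.1 | 3.5 / 9.4 / 16.5 / 25.3 |
| 0.3 | 4.7 / 13.5 / 22.9 / 34.3 | 5.3 / 14.6 / 23.6 / 34.9 |

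At slope 0.2, at least one of the three specific effects is flagged in 23.1% of trials at ICC 0.02 and 38.5% at ICC 0.05.

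**Step 3: sensitivity.**
- Outcome scale (slope 0.2). The mediators explain 0.2² × (3 + 6 × 0.5) = 0.24, so a unit-variance outcome has residual variance 0.76. On that scale a repeat gave specific-effect rates of 9.4 / 16.3% at ICC 0.02 / 0.05. With residual variance 1 it gave 7.7 / 13.4%, and 12.6 / 19.6% for the total effect.
- Mediator correlation (slope 0.2, ICC 0.02 / 0.05). At 0.3: specific 10.2 / 18.6%, total 10.8 / 20.9%. At 0.7: specific 6.6 / 11.8%, total 12.6 / 21.6%.
- One mediator, slope 0.4, clustering in the mediator only: interval coverage is 94.1% at ICC 0, then 89.4 / 86.9 / 76.5 / 64.2% at ICC 0.01 / 0.02 / 0.05 / 0.10.

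**Step 4: alternatives under the same null.**
- ASP-mean differences for the first paths, drawn jointly from a multivariate t with 4 df, with within-ASP slopes (4,000 draws): 0.7 to 5.3% in every cell.
- Resampling whole ASPs within arm: 7.8 to 21.0% for specific and 13.6 to 20.8% for total effects. Three ASPs give only 10 distinct resamples per arm.

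**Step 5: the slope assumption.** One mediator, ICC 0.05, program effect 0.4.
- Within-ASP slope 0.2, between-ASP slope 0.5: the true indirect effect is 0.4 × 0.5 = 0.20. The ASP-level method averages 0.080 and the pooled youth-level estimate 0.084.
- Within 0.4, between 0: the truth is 0. The two average 0.161 and 0.156, and the ASP-level interval excludes zero in 28% of trials.

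**The case against.** The strongest reply is that this is silence, not a stated error. The plan never says youths will be resampled, and it defers to methods papers whose treatment of clustering cannot be seen from the documents. That is true, and every rate above is conditional on a youth-level bootstrap. But a general citation does not fix a resampling unit, and nothing else in the plan brings ASP into this analysis.

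Second, the aim is exploratory in a feasibility trial, and no decision rule depends on it. This stands, and it limits the priority. It does not make a too-narrow interval acceptable, since readers of an exploratory estimate rely on its width.

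Third, the ICC, slopes, mediator correlation and outcome scale are all assumed, and adjusting for baseline values could leave a low residual ICC. This also stands. At ICC 0 there is no material inflation, and at slope 0.1 the specific effects pass 5% only at ICC 0.10.

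Fourth, the root is shared with the Primary Aim 2 ANCOVA. That is so, and the two should be corrected together. Adding ASP to the ANCOVA would still leave the bootstrap unit open.

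Fifth, a 4-df Monte Carlo interval is one choice among several. Figure 2 shows ASPs entering as three cohorts of two; adjusting for cohort would leave 6 − 4 = 2 df. Both points are fair.

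**Conclusion.** The concern holds. Read as an ordinary path model with an ordinary bootstrap, Secondary Aim 3 would give intervals that are too narrow whenever the mediators cluster by ASP and their slopes are not near zero.

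At slope 0.2 and ICC 0.02 to 0.05, the nominal 5% error becomes roughly 12 to 22% for the total effect and 9 to 17% for each specific effect. With outcome residual variance 1 it is about 13 to 20% and 8 to 13%. The direction is secure; the size depends on values the documents do not give. Priority is low to moderate, because the aim is exploratory and secondary.

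**What to change.** At minimum, state under Secondary Aim 3 how ASP enters the path model and what is resampled, and make the matching change in Primary Aim 2. A concrete version:

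- Estimate the treatment-to-mediator paths at ASP level with about 4 df (fewer if cohort is adjusted for). ASP means were the form simulated; an ASP random effect is an alternative that was not.
- Include ASP in the mediator-outcome model. With ASP as a fixed effect, the treatment term drops out of that model.
- Form intervals for total and specific indirect effects by Monte Carlo, drawing the three first paths jointly from a t distribution with 4 df.
- Do not rely on resampling youths, or on resampling whole ASPs with three per arm.
- State that a within-ASP slope gives the indirect effect only if within- and between-ASP slopes are equal. Six ASPs cannot check this well: intercept, treatment and three mediators leave 6 − 5 = 1 df.
- Report the results as exploratory estimates with ASP-level uncertainty.

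**Cost.** Plan wording and modest programming; no new data. Intervals widen: with no program effect and slope 0.2, the median total-effect width goes from 0.29 to 0.48 at ICC 0.02 and from 0.29 to 0.60 at ICC 0.05. Detection falls. With a 0.4 SD program effect on each mediator and slopes of 0.2, the total effect is found in 70 / 52 / 33 / 23% of trials at ICC 0 / 0.02 / 0.05 / 0.10. The youth-level bootstrap finds it in 92 / 86 / 78 / 77%, but those rates include inflated error. For specific effects the rates are 36 / 25 / 17 / 12% against 58 / 54 / 50 / 50%.

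The change corrects the error bars only. If within- and between-ASP slopes differ, the bias remains, about as large as in the pooled youth-level estimate. Error control then fails once the program moves the mediators.
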